# 7.6 Assessments – Observational Component

#### 7.6.1 Medical History & Demographics

A medical history and the patient's demographics will be taken within 28 days of registration including the following:

- Age
- Sex
- Disease type (current and prior)
- Previous medical conditions
- Previous treatments
- Cytogenetic status

Disease status

# 7.6.2 Disease Assessment

The blast count from the most recent available routine bone marrow or blood test performed prior to registration will be used to assess patient eligibility (blasts ≥10%), stratify the patient into MPN-AP or MPN-BP at baseline and determine the response criteria to be used during the trial. The bone marrow blast assessments recorded on the Baseline Form should be consistent with the stratification reported on the Eligibility Form.

Patients will have their disease assessed after 3, 6 and 12 months on the study according to the following criteria (using patient's most recent available routine bone marrow):

- Patients with ≥20% bone marrow blasts at baseline (MPN-BP) will be analysed using the "proposed criteria for response assessment in patients treated in clinical trials for MPNs in blast phase (MPN-BP): Formal recommendations from the post-MPN acute myeloid leukaemia consortium"[1]
- Patients with <20% bone marrow blasts at baseline (MPN-AP) will be analysed using the IWG criteria for MDS patients [2]

Both criteria can be found in Appendix 1.

Information on any treatments received by the patient will also be collected at 3, 6 and 12 month follow-up visits.

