1. Every effort should be made for patients to attend on the scheduled visit days. However, if a patient is unable to attend on the specified day, assessments may be scheduled for +/- 3 days

2. The physical examination and peripheral blood smear may be performed from day 22 of the preceding cycle to the start of the next cycle at local discretion

- 3. Women of child bearing potential only
- 4. Or earlier when there is evidence of remission or progression in the peripheral blood
- 5. Research samples should be taken between days 22-25 (or on a Monday Thursday at baseline) so that they can be received by the biobank. Both research samples (bone marrow and blood samples) should be collected on the same day
- 6. For patients continuing trial treatment beyond cycle 6, bone marrow aspirate, trephine and disease assessments are recommended every 3 months and at progression/relapse. Patients will have a final disease assessment when the additional treatment stops using the information of the most recent previous bone marrow obtained
- 7. The haematology and biochemistry assessments can be performed between days 22-25 to coincide with the collection of research blood and bone marrow samples or safety bloods
- 8. Dose modifications permitted in accordance with section 7.8 of the protocol after cycle 1
- 9. Administered at Chief Investigator's discretion following 6 cycles of combination treatment if patient obtaining clinical benefit
- 10. Patients will be followed up for a minimum of 12 months from study entry for survival and outcome data

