# SCHEDULE OF ASSESSMENTS – OBSERVATIONAL COMPONENT

Study schedule 	At registration	End of Month 3	End of Month 6	End of Month 12			
Informed consent	x						
Medical History & Demographics	x						
Information on further treatment		x	x	x			
Collection of routine full blood count results	x	x	x	x			
Collection of routine peripheral blood smear results (blast assessment)	Results to be collected if assessment performed as part of routine clinical practice						
Disease Assessment		x	x	x			
Quality of Life Assessment (optional)	x	x	x				
Blood Samples for Biobanking (optional)	x	x	x				
Bone marrow for Biobanking (optional)	Sample to be collected if assessment performed as part of routine clinical practice						
Nail clippings and/or saliva collection for germline DNA (optional)	x						

1. Efforts should be made to perform assessments during patient's routine visits rather than asking the patients to attend clinic for extra visits. Assessments should be performed as closely as possible to the schedule outlined above.

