# **Observational Component**

- Age ≥16 years old
- A prior diagnosis of ET, PV or MF with one of the following:
  - ≥10% blasts in blood or bone marrow with or without dysplastic changes (MPN-AP) at baseline
  - ≥20% blasts in blood or bone marrow (MPN-BP) at baseline
- Patients who are unwilling/unable to enter the interventional component and/or fail the interventional component entry criteria. This can include patients previously treated post transformation into MPN-AP/MPN-BP, or entered into studies with more aggressive therapy such as AML 17/19 as well as those receiving palliation only.
- Able to give valid informed consent

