#### 12.2.1.2 Secondary outcome measures

The following will be analysed for patients in the interventional component:

- Best response following 3 and 6 cycles of treatment. Response will be assessed according to the following criteria:
  - Proposed criteria for response assessment in patients treated in clinical trials for MPNs in blast phase (MPN-BP): Formal recommendations from the post-MPN acute myeloid leukaemia consortium" (for patients with ≥20% bone marrow blasts at baseline)[1]
  - International Working Group (IWG) response criteria in myelodysplasia (for patients with <20% bone marrow blasts at baseline)[2]

In order to assess disease response, bone marrow, peripheral blood and spleen/liver assessments should be performed during days 22-25 of cycle 3 and cycle 6.

• Achievement of RBC transfusion independence after completion of cycles 3 and 6 compared to baseline.

RBC transfusion dependence is defined as transfusion of  $\geq 2$  RBC units in the 8 weeks prior to registration at baseline, and as transfusion of  $\geq 2$  RBC units in the 8 weeks prior to cycle 3-day 28 or cycle 6-day 28 for subsequent assessments.

• Achievement of platelet transfusion independence after completion of cycles 3 and 6 compared to baseline.

Platelet transfusion dependence is defined as transfusion of  $\geq 1$  platelet units in the 4 weeks prior to registration at baseline, and as transfusion of  $\geq 1$  platelet units in the 4 weeks prior to cycle 3-day 28 or cycle 6-day 28 for subsequent assessments.

- Change in the proportion of RBC or platelet transfusion-dependent patients after completion of cycles 3 and 6 compared to baseline as defined above.
- Change in palpable splenomegaly or hepatomegaly after completion of cycles 3 and 6 compared to baseline

Size of palpable spleens will be measured below the left costal margin and reported in cm Size of palpable livers will be measured below the right costal margin and reported in cm

- Duration of Complete Response (CR) or Partial Response (PR) according to established criteria
   [1] [2]
- 12 months Progression-free survival (PFS)
- 12 months Leukaemia-free survival (LFS)

- 12 months Overall survival (OS)
- Duration of trial treatment
- Mean change in haemoglobin level from baseline to end of cycles 3 and 6 (cycle 3-day 22-25 or cycle 6-day 22-25)
- Mean change in platelet count from baseline to end of cycles 3 and 6 6 (cycle 3-day 22-25 or cycle 6-day 22-25)

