# **APPENDIX 1 – RESPONSE ASSESSMENT**

Proposed criteria for response assessment in patients treated in clinical trials for MPNs in blast phase (MPN-BP): Formal recommendations from the post-MPN acute myeloid leukaemia consortium - For patients with ≥20% bone marrow blasts at baseline

Myeloproliferative neoplasm in blast phase (MPN-BP) response categories.

Complete molecular response (CMR)	
Description	Complete remission of both leukemia and MPN without detectable molecular markers associated with either leukemia or MPN
Hematologic profile	ANC > 1000 Hemoglobin > 10 g/dL Platelets > 100 × 10  /L Absence of leukoerythroblastosis 
Spleen	Non-palpable
Bone marrow	Cellularity appropriate for age Resolution of abnormal morphology Blasts ≤ 5% b ≤Grade 1 marrow fibrosis
Cytogenetics Molecular markers	Normal karyotype c Loss of any previously documented markers associated with either the leukemic or MPN clone d
Complete cytogenetic response (CCR) Description	Complete remission of both leukemia and MPN with detectable molecular markers associated with either leukemia or MPN
Hematologic profile	ANC > 1000 Hemoglobin > 10 g/dL Platelets > 100 × 10  /L Absence of leukoerythroblastosis a
Spleen	Non-palpable
Bone marrow	Cellularity appropriate for age Resolution of abnormal morphology Blasts ≤ 5% b ≤Grade 1 marrow fibrosis
Cytogenetics Molecular markers	Normal karyotype c Residual expression of MPN/leukemia associated gene mutations (e.g. JAK2V617F, MPL515L/K) d
Acute leukemia response-complete (ALR-C) Description Hematologic profile Spleen Bone marrow Cytogenetics Molecular markers	Complete remission of leukemia with residual MPN features Absence of blasts  <25% increase in spleen size by palpation or imaging if baseline spleen <10 cm or <50% if baseline spleen $\geq$ 10 cm Blasts $\leq$ 5% Loss of cytogenetic abnormality associated with leukemic clone, may have persistent abnormality associated with MPN Loss of any previously identified markers in leukemic clone, may have persistent molecular markers associated with MPN 

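### Observational response can be scored on a marrow taken before registration, and section 7.6.2 gives conflicting blast rules for phase and response criteria

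*Protocol*

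**What the plan says.** **Follow-up marrow.** Section 7.6.2 assesses observational patients at 3, 6 and 12 months "using patient's most recent available routine bone marrow". The observational schedule of assessments has a disease assessment at each of those times but no marrow examination. Its only marrow entry is for biobanking: "Sample to be collected if assessment performed as part of routine clinical practice".

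**Baseline and phase.** Section 4.1 admits observational patients on blood or marrow blasts. The accelerated-phase line is "≥10% blasts in blood or bone marrow with or without dysplastic changes (MPN-AP) at baseline" and the blast-phase line starts at 20%, also in blood or marrow. Eligible patients include previously treated patients "as well as those receiving palliation only". Section 7.6.2 opens in the same spirit: "The blast count from the most recent available routine bone marrow or blood test performed prior to registration will be used" for eligibility, for the MPN-AP/MPN-BP split and for choosing the response criteria. The two bullets that follow use marrow blasts only: 20% or more is labelled MPN-BP and scored by the post-MPN AML consortium criteria; below 20% is labelled MPN-AP and scored by the IWG criteria.

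**Interventional component.** Section 7.5.7 requires a marrow within 28 days before registration and schedules further marrows at days 22-25 of cycles 3 and 6. Section 12.2.1.2 lists "Duration of Complete Response (CR) or Partial Response (PR) according to established criteria", citing both criteria sets.

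**The concern.** A response assessment compares a later state with baseline. If the later marrow may be the baseline marrow, the comparison is empty for the marrow part of the criteria, yet a response category can still be recorded. The same lack of a window lets a 3-month marrow stand for the 12-month state, so an earlier response could also be carried forward past its loss.

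The blast rule decides which of two quite different criteria sets applies and which phase a patient is reported under. Section 2.2 gives the observational component the aim of describing treatment and outcome in MPN-AP and MPN-BP patients. If label and criteria can disagree for one patient, two people following the protocol can tabulate that patient differently. At stake is the descriptive account of response by phase in up to 30 patients.

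**Working it through.** The protocol gives no figure to reproduce on this point, so the check sets the rules side by side.

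**1. A patient whose latest marrow is the baseline marrow.** Let baseline marrow blasts be b. The follow-up value is also b, so the change is (b − b)/b = 0%. In Appendix 1:

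- Consortium criteria (for b of 20% or more): CMR, CCR and ALR-C all need marrow blasts of 5% or less, and ALR-P needs a fall of more than 50%. None can be met.
- IWG criteria: partial remission and marrow CR need a fall of at least 50%, and complete remission needs 5% or less. For any b above 5%, none can be met.
- Both sets define stable disease as no partial response and no progression over about 8 weeks.
- Progression does not always need a marrow. The consortium set also uses blood blasts and spleen size. The IWG set also uses falls in granulocytes, platelets or haemoglobin and transfusion dependence, and counts death during treatment as failure. Section 7.6.3 collects blood counts at 3, 6 and 12 months, and blood blasts where a smear was done routinely. The observational schedule lists no spleen examination.

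So a true marrow response is lost, marrow progression is unseen, and the default is stable disease unless another route shows progression.

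**2. Illustration of the size.** Let s be the share of true responders whose latest marrow predates their response. The documents give no value for s; 0 to 60% is an assumption. Scored rate = true rate × (1 − s). For true rates I use the 54% overall response and 24% CR that section 1.1 quotes for a historical azacitidine cohort. Observational patients receive varied treatment, so these are not predictions.

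| s | true 54% | true 24% |
|---|---|---|
| 0% | 54% | 24% |
| 20% | 0.54 × 0.8 = 43% | 0.24 × 0.8 = 19% |
| 40% | 0.54 × 0.6 = 32% | 0.24 × 0.6 = 14% |
| 60% | 0.54 × 0.4 = 22% | 0.24 × 0.4 = 10% |

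**3. Phase label against criteria set, observational patients.** The third column takes the higher of the two counts, because section 4.1 accepts either source.

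| Blood blasts | Marrow blasts | Phase by 4.1 | 7.6.2 bullets |
|---|---|---|---|
| 15% | 15% | MPN-AP | MPN-AP, IWG |
| 15% | 25% | MPN-BP | MPN-BP, consortium |
| 25% | 25% | MPN-BP | MPN-BP, consortium |
| 25% | 12% | MPN-BP | MPN-AP, IWG |
| 15% | none | MPN-AP | fits neither |
| 25% | none | MPN-BP | fits neither |

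The rules conflict when blood blasts are 20% or more and marrow blasts are below 20%. They give no bullet when there is no marrow. In the fourth row the patient also meets the MPN-AP entry line literally, because that line has no ceiling and so contains the MPN-BP line; the interventional criteria use 10-19%. Section 7.6.2 further asks that baseline marrow blasts agree with the stratification on the Eligibility Form, which the fourth-row patient cannot satisfy if stratified on blood.

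**4. Duration of response, interventional.** The consortium categories are CMR, CCR, "Acute leukemia response-complete (ALR-C"), ALR-P, stable and progressive disease. None is named CR or PR, and the protocol gives no mapping.

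**The case against.** The strongest reply is that this is a descriptive side cohort: no scheduled study visits (section 1.2.2), no comparison with the interventional component (sections 3.2 and 12.1), no hypothesis test (section 12.3) and no duration-of-response outcome. Detail could be settled in the SAP. The description and the lack of comparison are correct and limit the importance. The SAP argument does not dispose of the point: the marrow rule and the two blast rules are stated in the protocol, and they give an empty comparison in one case and conflicting answers in the other. If the marrow date is not captured at the time, a later analysis plan cannot restore it.

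Several stronger readings are tempting, and the documents do not support them:

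- *Every patient without a repeat marrow is stable by construction.* No. Blood counts, blood blasts, spleen and clinical events can show progression. Nor is there a basis for a percentage, since the frequency of repeat marrows is not given.
- *Interventional response may also rest on a pre-registration marrow.* The final assessment after extended treatment is made "using the information of the most recent previous bone marrow obtained", which may be out of date. For a patient followed to schedule, though, that marrow is an on-study one, and cycle 3 and 6 responses have their own scheduled marrows.
- *The blast-rule conflict affects interventional patients.* They enter on marrow blasts alone, so label and criteria agree.
- *Response cannot be computed for MPN-BP.* Section 12.3 reports best response by category, which needs no CR or PR label. Appendix 1 describes CMR, CCR and ALR-C as kinds of complete remission. Only duration of response is touched, only among responders, and the SAP could settle the mapping.
- *The 10%/20% overlap lets in the wrong patients.* It changes nobody's eligibility, only the label.

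**Conclusion.** The point holds for the observational component. As written, section 7.6.2 allows a pre-registration marrow to be scored as follow-up, which hides marrow response and leaves stable disease as the default unless progression shows elsewhere. It also gives conflicting rules for phase and criteria set when blood blasts are 20% or more with marrow blasts below 20%, and no bullet for patients without a marrow. The number affected cannot be derived from the documents: neither the share without a repeat marrow nor the share with discordant counts is given. Under the assumed range in the illustration, a true 54% response rate could be scored as low as 22%, but that shows direction and scale only. The primary MTD outcome and the interventional cycle 3 and 6 responses are unaffected. The missing CR/PR mapping for MPN-BP is a minor labelling gap in one interventional secondary outcome.

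**What to change.** In section 7.6.2 and the matching observational text:

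1. Score marrow response only from a marrow dated after registration and within a stated window of the 3-, 6- or 12-month time point. Otherwise record not evaluable for response, with progression on blood or clinical criteria still counted. Record the marrow date on the form.
2. Set the observational MPN-AP line to 10-19%, so that it no longer contains MPN-BP.
3. Use one blast rule, for example the higher of blood and marrow, for both the phase label and the criteria set, and align the bullets and the Baseline Form check with it.
4. As a minor addition to section 12.2.1.2 or the SAP, state which of CMR, CCR, ALR-C and ALR-P count as CR and as PR for duration of response.

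The cost is wording and a date field. More observational patients will be not evaluable for response, and their number should be reported beside the response table. No extra marrow is required of any patient.

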# 7.6.3 Haematology

The results of full blood counts obtained during routine visits at registration and after 3, 6 and 12 months on the study should be recorded on the relevant CRF.

Full blood counts include:

- Red blood cells
- Haemoglobin
- White blood cells

- Haematocrit
- Absolute neutrophil count
- Lymphocytes

Platelets

Blast assessments on peripheral blood smears performed as part of routine clinical practice at registration and after 3, 6 and 12 months on the study should be recorded on the relevant CRF.

# 7.6.4 Quality of Life Assessment

All patients in PHAZAR will be asked to complete QoL questionnaires.

The EORTC QLQ-C30, EQ-5D and Myeloproliferative Neoplasm Self-Assessment Form (MPN-SAF) questionnaires (see Appendix 6) will be used to assess QoL and health outcome at registration and after 3 and 6 months.

- The QLQ-C30 is composed of both multi-item scales and single-item measures. These include five functional scales (physical, role, emotional, cognitive and social), three symptom scales (fatigue, pain, and nausea and vomiting) a global health status/QoL scale, and six single items.
- The EQ-5D is a standardised instrument for use as a measure of health outcome. The EQ-5D-5L descriptive system comprises of five dimensions (mobility, self-care, usual activities, pain/discomfort, anxiety/depression).
- The MPN-SAF was created to function as a single instrument of patient-reported symptoms for the entire spectrum of patients with MPN. It is a comprehensive and reliable and concisely assesses the prevalence and severity of symptoms of MF, PV, and ET, not captured in other instruments.

The three questionnaires are to be administered at the clinic under the supervision of study staff.

# 7.7 Sample Collection

# 7.7.1 Samples from patients on the interventional component

Samples are compulsory for patients on the interventional arm.

# Germline Samples

Patients will have toe nail clippings and/or saliva collected within 28 days prior to registration.

# Blood Samples

20 ml blood samples will be collected within 28 days prior to registration, during days 22-25 of cycles 3 and 6 (and on the same day as the bone marrow samples) or sooner if there is evidence of remission or progression in the peripheral blood. N.B. samples must be taken Monday to Thursday only to allow for processing at the biobank. Allele burden will be analysed at baseline, at 3 months and at 6 months at the Weatherall Institute of Molecular Medicine (Oxford).

# Bone Marrow Aspirate and Trephine Samples

Up to 10 ml of bone marrow aspirate and a bone marrow trephine sample will be collected when trial bone marrow assessments are performed (within 28 days prior to registration and during days 22-25 of cycles 3 and 6 or sooner if there is evidence of remission or progression in the peripheral blood). For patients continuing trial treatment beyond cycle 6, bone marrow aspirate and trephine samples are

**Protocol** 

recommended every 3 months N.B. samples must be taken Monday to Thursday only to allow for processing at the biobank.

#### Optional Historic Bone Marrow Trephine Samples

With consent and if obtainable, approximately 15 historic unstained bone marrow trephine sections prepared during the chronic phase of the patient's disease will be requested at study entry.

#### 7.7.2 Samples from patients on the observational component

All samples are optional for patients on the observational arm.

#### Germline Samples

Patients will be asked to consent to have toe nail clippings and/or saliva collected at the time of registration.

#### Blood Samples

Patients will be asked to consent to a 20 ml blood sample being collected at the time of registration, after 3 months and after 6 months. Allele burden will be analysed at baseline and at 3 and 6 months at the Weatherall Institute of Molecular Medicine (Oxford).

#### Bone Marrow Aspirate and Trephine Samples

Patients will be asked to consent to an additional 10 ml of bone marrow aspirate and a bone marrow trephine sample being collected and sent to the Weatherall Institute of Molecular Medicine from any routine bone marrow assessments conducted during the 6 month study period.

#### Historic Bone Marrow Trephine Samples

With consent and if obtainable, approximately 15 historic unstained bone marrow trephine sections prepared during the chronic phase of the patient's disease will be requested at study entry.

# 7.7.3 Sample processing

All samples should be sent to the Weatherall Institute of Molecular Medicine at the following address:

Tissue Bank Technician MDSBio Study Room 326 Molecular Haematology Unit Weatherall Institute of Molecular Medicine John Radcliffe Hospital [name]

Address labels for the Weatherall Institute of Molecular Medicine will be provided in the Investigator Site file. Samples should be packaged and posted as per the table below:

Sample	Collection
Toe nails	Specimen Pot
Saliva	Oragene saliva kit
20 ml blood sample	EDTA tube(s)
10 ml Bone Marrow Aspirate	EDTA tube(s)
Bone Marrow Trephine	Slide box

Special delivery boxes, first class boxes, specimen pots, Oragene saliva kits and slide boxes will be provided by the trials unit.

